6.3 Treatments Administered

Part 1 of the study will investigate ADCT-301 administration every 3 weeks. In Part 2, all patients will be assigned to the dose level identified in Part 1 by the DESC. ADCT-301 will be administered on Day 1 of each cycle as a 1-hour IV infusion. If ADCT-301 is well tolerated after the first cycle, the infusion duration may be shortened as a 30 minutes IV infusion for subsequent cycles, at the Investigator's discretion.

Variation in infusion times due to minor differences in IV bag overfill/ underfill and the institution's procedure for flushing chemotherapy lines will not result in protocol deviations. Prophylactic antiemetic medications, electrolyte supplementation, and other standard supportive care measures may be administered according to standard treatment center protocols.

Although the study patient population has a low risk for development of tumor lysis syndrome (TLS) compared to patients with acute disease,¹ patients should be observed for development of TLS and treated according to standard treatment center protocols.

Because of non-clinical observations related to nephropathy and adrenal gland changes, adequate patient hydration (e.g., 8 to 10 glasses of water or equivalent per day) is recommended for patients receiving ADCT-301.

Available pre-clinical data on ADCT-301 does not suggest a photosensitivity concern, based on the lack of any signals in the rat and monkey toxicology studies with ADCT-301 and the non-clinical experience with SG3199, including a QWBA study indicating no specific accumulation to melanin containing tissues, skin or eyes.

However, skin rash has been reported in the ADCT-301 program, as well as with another investigational agent containing the same pyrrollobenzodiazepine warhead.³ The rash has been limited to areas at risk for sun exposure; it is therefore recommended that precautions are taken to avoid prolonged exposure of skin to direct sunlight.

6.4 Dose Delays and Modifications

The Investigator may suspend ADCT-301 dosing for up to 21 days for any patient who experiences a protocol-defined DLT during any treatment cycle.

At the discretion of the Investigator, the dose may also be delayed for up to 21 days for any other toxicity of any grade.

Resumption of dosing with ADCT-301 after any suspension, even when longer than 21 days, is at the discretion of the Investigator, in consultation with the Sponsor, based on assessment of the patient's clinical condition and whether or not the patient is deriving potential clinical benefit from treatment with ADCT-301. Following recovery to Grade 1 or baseline, treatment may resume at the Investigator's discretion.

Patients who resume treatment following a dose delay may, at the discretion of the Investigator, have their dose reduced by 1 dose level in either part of the study. If toxicity reoccurs at a severity that would mandate a dose delay, then the dose may be further reduced 1 dose level. If toxicity reoccurs at such level, then the patient is to be discontinued from treatment. Dose re-escalation is allowed at the investigator's discretion, at maximum to the dose level the patient was initially assigned to.

Patients experiencing certain types of infection during the course of participation in this clinical study also must delay further dosing, as stipulated in [Section 7.3.4.5](#).

Patients experiencing any autoimmune toxicities (e.g. endocrinopathies) \geq Grade 1 need to be followed at least weekly to quickly detect deterioration and modify dosing as per DLT criteria (can be done by telephone unless symptoms worsen).

Patients experiencing the following significant toxicities will be immediately and permanently withdrawn from treatment with ADCT-301:

- Any patient who experiences a Grade 3 or higher hypersensitivity reaction, regardless of premedication, during any cycle of treatment per CTCAE definitions ([Appendix 13.4](#)).
- Any patient who experiences a recurrent Grade 3 or 4 toxicity excluding hematological toxicity.
- Any patient who requires a dosing delay $>$ 21 consecutive days from the planned Day 1 dosing at any time during treatment (except in case of potential patient benefit, which must be approved by the Sponsor).

Neurological toxicities: dose delay/permanent discontinuation

Patients experiencing any new neurological toxicities \geq Grade 1, not explained by previous medical history, that could be linked to or may be an early indicator of polyradiculopathy/GBS, such as ascending (bilateral) sensory loss or motor weakness, need to be immediately evaluated by a neurologist and dosing of ADCT-301 needs to be delayed until polyradiculopathy/GBS is ruled out. Should further clinical, radiologic, or laboratory evidence support the diagnosis of polyradiculopathy/GBS with the level 1 of diagnostic certainty ([Appendix 13.6](#)), treatment with ADCT-301 must be stopped and patient must be permanently discontinued.

Patients with Grade \geq 3 neurologic toxicities defined as peripheral sensory and peripheral motor neuropathies must be permanently discontinued.

Other new neurological findings not explained by previous medical history increase of \geq 1 grade over baseline will result in dose delay; dosing may be resumed after resolution to baseline, at the investigator's discretion. The patient must be carefully monitored at least weekly until such resolution (can be done by telephone unless symptoms worsen).

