4.1.2 Dose Expansion (Part 2)

In Part 2 (expansion), patients will be assigned to receive the recommended dose(s) of ADCT-301, as determined by the DESC during Part 1 of the study.

The following dosing regimen(s) may be investigated based on safety and PK emerging information:

- 45 µg/kg every 3 weeks for 3 cycles followed by 30 µg/kg every 3 weeks for patients who have not progressed.
- 45 µg/kg every 3 weeks for 3 cycles followed by 20 µg/kg every 3 weeks for patients who have not progressed.
- 45 µg/kg every 3 weeks for 4 cycles followed by 30 µg/kg every 3 weeks for patients who have not progressed.
- 45 µg/kg every 3 weeks for 4 cycles followed by 20 µg/kg every 3 weeks for patients who have not progressed.

The patient population (e.g., disease subtypes) to be enrolled in Part 2 (expansion) may be refined based on results and observations from Part 1.

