13.5 Appendix: Dose Escalation Scheme Report

13.5.1 Overview

A primary objective of the dose escalation portion of the study is to estimate an MTD. The MTD will be the highest safe dose that has at least a 60% probability that the dose limiting toxicity (DLT) rate is < 30%. The DLT observation period is 1 cycle.

Dose escalation will begin with the 3 µg/kg starting dose (Dose Level 1). There will be 33 dose levels including all dose levels from:

- 0.003 to 0.02 mg/kg in increments of 0.001
- 0.02 to 0.05 mg/kg in increments of 0.005
- 0.05 to 0.10 mg/kg in increments of 0.01
- 0.10 to 0.30 mg/kg in increments of 0.05

Dose escalation will be conducted according to a continual reassessment method (CRM). Non-DLT toxicity events (i.e. Grade 2 or higher toxicities) will inform the probability of DLT at each dose level. Dose escalation is also conducted according to a set of rules that govern entry into the study and assignment of dose level. These rules allow that untried dose levels may be skipped. The trial is continuously monitored for safety and early stopping for successfully identifying the MTD.

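### Protocol 6.4 gives two unranked rules for recurrent non-hematologic Grade 3–4 toxicity and does not fit its dose-reduction steps to the optional Part 2 step-down regimens

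*Protocol*

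**What the plan says.** **Reduction ladder (Protocol 6.4).** A patient who resumes after a delay may, if the investigator chooses, "have their dose reduced by 1 dose level in either part of the study". On recurrence: "If toxicity reoccurs at a severity that would mandate a dose delay, then the dose may be further reduced 1 dose level". Discontinuation is required only at the next recurrence: "If toxicity reoccurs at such level, then the patient is to be discontinued from treatment". The ladder has no grade limit and does not separate hematologic from other toxicity.

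**Withdrawal list (same section).** Certain patients must come off ADCT-301 immediately and permanently. One entry reads: "Any patient who experiences a recurrent Grade 3 or 4 toxicity excluding hematological toxicity". SAP 4.3 item 3 repeats this as a mandatory-withdrawal criterion and makes failure to withdraw a pre-defined important deviation.

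**Delays.** For dose-limiting toxicities (DLTs): "The Investigator may suspend ADCT-301 dosing for up to 21 days for any patient who experiences a protocol-defined DLT". Delay for any other toxicity is also at the investigator's discretion. Section 6.4 mandates delay only for certain infections (with 7.3.4.5) and certain neurological findings.

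**Re-escalation.** This is left to the investigator, "at maximum to the dose level the patient was initially assigned to". Section 4.1.1 rules out intra-patient escalation during the study.

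**Dose levels.** Protocol 13.5.1 holds the only list: "There will be 33 dose levels including all dose levels from" 3 to 300 µg/kg, with spacing that widens up the range. Protocol 4.1.2 names four regimens that may be used in Part 2. Each starts at 45 µg/kg for 3 or 4 cycles and then steps down to 30 or 20. One, for example, gives 45 µg/kg "every 3 weeks for 3 cycles followed by 30" µg/kg. Sections 6.1 and 6.3 describe Part 2 assignment as a single dose level.

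**The concern.** Take a patient with a Grade 3 non-hematologic DLT who resumes one level lower and has the same event again. One part of 6.4 allows re-treatment at a further reduced dose; another requires that treatment stop for good. A site that uses the permission commits a deviation that the SAP has defined in advance. This is a patient-safety instruction and should have one answer.

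The second issue arises if Part 2 uses a step-down regimen. The reduction rule is stated for both parts of the study, but its unit, the dose level, is defined only for the escalation. The re-escalation ceiling points to the dose assigned at the start, and the regimens themselves move patients off that dose by plan. Tolerability in Part 2 is a primary objective (Protocol 3.1), so the dose to be given after a toxicity should be readable from the protocol.

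**Working it through.** **1. Where the two rules in 6.4 overlap.** Consider toxicity that recurs after one delay and one reduction:

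| Recurrent event | Ladder | Withdrawal list | Result |
|---|---|---|---|
| Hematologic | further reduction permitted | expressly excluded | no conflict |
| Non-hematologic below Grade 3 (e.g. Grade 2 skin ulceration or peripheral neuropathy, both DLTs under 7.3.1.1) | further reduction permitted | not covered | no conflict |
| Non-hematologic Grade 3–4 | further reduction permitted | withdrawal required | both apply, unranked |

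Grade 3 or higher hypersensitivity and Grade 3 or higher peripheral neuropathy end treatment at first occurrence under their own rules in 6.4, so they never reach the ladder.

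**2. The ladder's trigger.** The second step depends on a severity that would mandate a delay. Delay for DLTs and for other toxicity is optional, so strictly read the trigger fits only the infections and neurological findings for which delay is mandated. That reading narrows the overlap in the third row, but it also leaves the second step silent on most recurrent DLTs, including hematologic ones.

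**3. Rebuilding the list of levels (13.5.1), in µg/kg.**

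- 3 to 20 by 1: 18 levels
- 25 to 50 by 5: 6 levels
- 60 to 100 by 10: 5 levels
- 150 to 300 by 50: 4 levels
- Total 18 + 6 + 5 + 4 = 33, which matches the protocol.

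**4. Size of a step.** Reduction = 1 − (lower dose / current dose).

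| Step | Basis | Reduction |
|---|---|---|
| 45 to 40 | one grid level | 1 − 40/45 = 11.1% |
| 45 to 35 | two grid levels | 1 − 35/45 = 22.2% |
| 30 to 25 | one grid level | 1 − 25/30 = 16.7% |
| 20 to 19 | one grid level | 1 − 19/20 = 5.0% |
| 45 to 30 | planned step-down (3 grid levels) | 1 − 30/45 = 33.3% |
| 45 to 20 | planned step-down (5 grid levels) | 1 − 20/45 = 55.6% |

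The planned steps are several times larger than one grid level, and 6.4 does not say how the two combine. Section 13.5.1 also allows levels to be skipped, so the levels tried in Part 1 may be sparser than the grid; the documents do not list them.

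**5. Re-escalation ceiling.** In all four regimens the starting dose is 45 µg/kg. After the planned step-down, a literal return to that dose is 45/30 = 1.5 or 45/20 = 2.25 times the scheduled dose. Section 4.1.2 limits 45 to 3 or 4 cycles, and 6.4 states no lower ceiling after step-down.

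**The case against.** **The ladder only permits; the list commands.** A site that withdraws the patient breaks neither sentence, and the SAP's word mandatory supports giving the list priority. The ladder keeps real scope for hematologic and lower-grade toxicity. All of this stands, so a reader who infers a flat contradiction, or a conflict for every Grade 3–4 toxicity, goes too far. But priority of the mandatory rule is the reader's inference; neither document states it.

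**The Part 2 points are conditional.** The four regimens are optional, and 6.1 and 6.3 speak of one dose level. The initially assigned level might mean the assigned regimen, a maximum is not an instruction to return, and nothing in 6.4 cancels the schedule in 4.1.2. The sentence in 4.1.1 sits in the Part 1 section and has its own exception for moving patients to the recommended dose. These points stand as limits. They do not supply the missing rule, because 6.4 expressly covers both parts and 4.1.2 lists no other regimens.

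**Oversight reduces the practical risk.** Resumption is decided in consultation with the sponsor, and the DESC includes investigators from each site, meets at least monthly and continues in Part 2. That is fair, but consultation does not replace a readable rule.

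**Conclusion.** The point holds in limited form. For recurrent non-hematologic Grade 3–4 toxicity, 6.4 permits a further reduction and also requires withdrawal, with no order of precedence. The SAP attaches an important deviation to one of the two courses. The ladder's trigger does not match the discretionary delays around it. If a step-down regimen is used, the relation of a one-level reduction (11% from 45, 17% from 30 or 5% from 20 on the grid) to the planned steps (33% or 56%) is unstated. The literal ceiling then allows 1.5 or 2.25 times the scheduled dose. The sizes assume that the 13.5.1 grid defines the levels and that a 4.1.2 regimen is in use.

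Three stronger inferences are not supported:

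- A reader might take 33% or 56% as alternative sizes of a one-level reduction. No text calls 30 or 20 the next level below 45; the grid gives 40.
- A reader might conclude that Part 2 discontinuation and reduction rates would reflect how sites read 6.4 rather than the drug. Delay and reduction are discretionary by design, and nothing in the documents sizes such an effect.
- A reader might treat the SAP's figure of 15% above planned dose as a tolerance that would hide a one-level error. SAP 4.3 gives it only as an example of an incorrect dose.

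**What to change.** Reconcile Protocol 6.4 with 4.1.1, 4.1.2, 6.1 and 6.3, and with SAP 4.3 items 3 and 4:

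- **(a)** Limit the ladder and the withdrawal list so that both cannot apply to the same event, and align the ladder's trigger with the delays that 6.4 actually mandates or permits.
- **(b)** State which list of doses a one-level reduction refers to in Part 2, and how a reduction combines with a planned step-down.
- **(c)** State the re-escalation ceiling after a planned step-down, and how it sits with the bar on intra-patient escalation in 4.1.1.

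Which rule, list and ceiling apply is for the sponsor and the DESC to decide. The cost is a protocol wording change with matching SAP text; it adds no patients, visits or data.

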6.5 Study Stopping Rules

The study will be paused if any of the following circumstances occur:

- \geq 30% of patients experience a specific Grade 4 or higher non-hematologic treatment-emergent AE.
- if any patient in Part 1 or Part 2 experiences a CTCAE Grade 5 AE, or 2 non-hematologic CTCAE Grade 4 AEs that are not attributable to the underlying disease, and for which relationship to ADCT-301 cannot be ruled out, within 30 days of their last dose of ADCT-301.

Furthermore, the Sponsor will notify regulatory agencies within 48 hours of being made aware of any new confirmed cases of GBS/polyradiculopathy to discuss, if appropriate, and determine whether or not the benefit-risk ratio has changed and dosing of additional patients and/or dosing of ongoing patients must be stopped. IRBs/IECs will be informed about the outcome of the assessment as appropriate.

6.6 Identity of Investigational Product

ADC Therapeutics will provide and distribute adequate supplies of ADCT-301 to the study sites. The following drug supplies will be used in the study:

| Product | Supplied As: |
|----------------|--|
| ADCT-301 | 10 mL glass vial at a deliverable volume of 5.4 mL at 6 mg/mL (equivalent to 30 mg ADCT-301) |

6.6.1 ADCT-301 Drug Product

ADCT-301 is a sterile formulation containing PBD-conjugated HuMax-TAC (DAR \geq 1), HuMax-TAC (DAR = 0), and SG3249. It is provided pre-formulated in 10 mL glass vials containing approximately 30 mg ADCT-301 per vial (deliverable volume 5.4 mL at 6 mg/mL).

6.7 Management of Clinical Supplies

6.7.1 Study Drug Packaging and Storage

ADCT-301 will be supplied in a labeled 10 mL stoppered glass vial and shipped by Fisher Clinical Services to the investigational site. Once the package arrives, the receiving site pharmacy will complete the enclosed procedures to acknowledge receipt.

All study drugs must be stored in a secure area (e.g., a locked cabinet). ADCT-301 should be protected from light and stored frozen (-65°C or below). ADCT-301 should be thawed under ambient conditions. After the vials have been completely thawed, they should be gently mixed by swirling to ensure homogeneity and visually inspected before use. The appropriate quantity of ADCT-301 will be removed from the vial with a syringe and diluted into a 50 mL IV bag containing 5% dextrose in water (D5W). The amount of the product to be diluted will depend on the dose level and the mass of the patient. Once the ADCT-301 has been transferred, the bag should be mixed to ensure homogeneity of the dosing solution. The contents of the IV bag will then be administered to the patient with a dosing pump per institutional guidelines for intravenous fluid (IVF) administration.

Additional instructions regarding study drug handling, storage, and preparation are included in the pharmacy manual.

6.7.2 Study Drug Accountability

The Investigator will maintain accurate records of receipt of all study drugs, including dates of receipt. In addition, accurate records will be kept regarding when and how much study drug is dispensed and used by each patient in the study. Reasons for departure from the expected dispensing regimen must also be recorded. All study drugs will be reconciled and retained or destroyed according to applicable regulations.

6.8 Overdose Management

An overdose is any dose of study treatment given to a patient that exceeds the dose described in the protocol. Any overdose, with or without associated AEs, must be promptly reported to the Sponsor. There are no data available to determine what effects and whether effects of an overdose can be reversed. Symptomatic treatment and standard supportive care measures for the management of this toxicity should be applied.

6.9 Treatment Compliance

Administration of the study treatments will be performed by the Investigator or a qualified designee; therefore, compliance will be verified by the study drug administration information.

6.10 Concomitant Treatment

All medications used within 14 days prior to Day 1 and during the treatment period are to be recorded in the eCRF. Concomitant medication information will be collected for 30 days following the patient's last dose of ADCT-301. This will include all prescription drugs, herbal products, vitamins, minerals, and over-the-counter medications. Any changes in concomitant medications will also be recorded in the patient's eCRF.

6.10.1 Prohibited During Study

- Other anticancer therapy, with the exception of hormonal therapy for maintenance treatment of breast and prostate cancer.
- Radiation therapy is prohibited during the first cycle of therapy. After the first cycle, radiation is permitted for palliative use only if documented radiographic disease progression is ruled out first.
- Other investigational agents.
- Chronic treatment with prednisone ≥ 40 mg/day or equivalent.
- Live vaccines.

6.10.2 Permitted During Study

After confirmation and documentation of eligibility, supportive care treatments (transfusions, etc.) can be prescribed as medically appropriate. Note: hematopoietic growth factors are permitted per American Society of Clinical Oncology guidelines; however, prophylactic use of growth factors is not allowed during the first treatment cycle.

If Grade 2 or higher infusion-related hypersensitivity reactions are observed in a patient at any time during the study, this patient must receive prophylactic treatment with all subsequent dosing as per [Section 6.2](#).

Concomitant steroid use is permitted as follows:

- Replacement doses of steroids for patients with adrenal insufficiency
- Intranasal, inhaled, topical steroids, or local steroid injections (e.g., intra-articular injection)

Patients scheduled to receive ADCT-301 are to be administered prophylactic steroid treatment as follows, unless contraindicated:

Dexamethasone 4 mg PO BID

- Day -1 (day prior to dosing – if possible)
- Day 1 (day of dosing; give at least 2 hours prior to administration when not given the day before; otherwise any time prior to administration)
- Day 2 (day after dosing)

Note: prophylaxis for hypersensitivity will supersede stipulations on dexamethasone prophylaxis.

In addition, spironolactone, at standard doses, may be instituted at any time for patients with weight gain greater than 1 kg (2.2 pounds) from Cycle 1 Day 1, new or worsening edema, and/or new or worsening pleural effusion. The dose of spironolactone should be titrated as clinically indicated. Additional diuretic support may be added if there is further increase in weight, edema or pleural effusion.

Any concomitant medication deemed necessary for the welfare of the patient during the study may be given at the discretion of the Investigator.

6.10.3 Diagnostic, Work-up, and Management of Polyradiculopathy/Guillain-Barré Syndrome

It is recommended starting management of polyradiculopathy/GBS with either intravenous immunoglobulin (IVIg) 0.4 g/kg/day for 5 days or plasma exchange (PLEX) once the diagnosis of polyradiculopathy/GBS has been considered by a neurologist; this would be at CTCAE Grade 2 symptoms for neuropathy or Score 1 as per GBS disability scale ([Appendix 13.7](#)).

Diagnostic workup should include:

- Neurology consultation
- MRI spine with and without contrast to rule out compressive lesion and evaluate for nerve root enhancement or thickening
- Electrodiagnostic studies (nerve conduction studies)
- Pulmonary function tests
- Lumbar puncture: CSF typically has albuminocytologic dissociation with protein elevation disproportionate to WBC—although note that CSF WBC are often elevated in GBS associated with immune checkpoint inhibitors
- Serum antibody testing for GBS (ganglioside antibodies) when possible

Management includes:

- IVIg or PLEX as above
- If IVIg and/or PLEX do not result in improvement, consider using steroids¹⁴
- Admission to inpatient unit with capability for rapid transfer to ICU-level monitoring
- Frequent focused neurological examination (at least twice daily)
- Frequent pulmonary function monitoring
- Monitoring for autonomic dysfunction
- Non-opioid management of neuropathic pain
- Treatment of constipation/ileus
- Anticoagulation
- Physical therapy

7 Study Assessments and Procedures

Patients will undergo the procedures at the time points specified in schedule of events ([Appendix 13.1](#)).

